### 3.6 Sub-group analyses

1. Sub-groups will be analyzed for primary analyses, secondary analyses and sensitivity analyses. We will conduct exploratory sub-group analyses including by:
  - a. **Sex:** Participants will be divided into groups by sex (male vs. female)
  - b. **Age:** Participants will be divided into age categories (e.g. younger vs. older)
  - c. **ART status:** Participants will be divided into groups by ART status (on ART vs. not on ART)
  - d. **Time on ART:** Participants will be categorized into groups by length of time on ART (e.g. newly initiated on ART vs. ART experienced patients)
  - e. **History of prior TB:** Participants will be categorized into groups by history of prior TB (prior TB vs. no prior TB)
  - f. **Level of reimbursement:** Reimbursement for clinic-related visits was adjusted throughout the course of the trial in response COVID-related travel increases and Uganda Institutional Review Board (**IRB**) minimum reimbursement requirements (levels: 15,000 Ugandan Shillings (**USh**), 20,000 USh, 30,000 USh)

### 3.7 Analysis of secondary outcomes

Secondary outcome analysis will include:

1. **Reach outcome(s):** 1) Unadjusted comparisons across arms, and 2) simple calculation of the proportion of patients randomized who accept treatment in each arm.
2. **Effectiveness outcomes:** 1) Occurrence of AEs across arms will be assessed using Chi-square tests and logistic regression; 2) Incidence of active TB will be assessed using Kaplan-Meier curves, log-rank tests, and Cox proportional hazards methods as appropriate. Assessment for active TB occurs at 15-16 months post enrolment. Survival analyses will include:
  - o An assessment of the incidence rate of TB, comparing across arms (DOT vs. SAT vs. Choice) using Kaplan Meier, time-to-event analyses. We will estimate the difference in the Kaplan Meier and Cox proportional hazard estimators for the survivor functions, comparing the arms to get hazard ratios and 95% CIs.
  - o An assessment of the incidence rate per arm by drug compliance, which will include for each arm: a comparison of the incidence of active TB in those within the arm that complete at least 11 of the 12 doses within the allotted 16 weeks vs. the incidence of active TB in those within the arm that complete  $\leq$ 10 doses of 3HP. We will estimate the difference in the Kaplan Meier and Cox proportional hazard estimators for the survivor functions, comparing the arms to get hazard ratios and 95% CIs.

3. **Adoption outcomes:** For each process metric, we will report the monthly proportion (and 95% CI) number, or median (interquartile range (IQR)) to assess the implementation of intervention components in each arm.
4. **Implementation outcomes:** Quantitative data will be assessed using multivariable regression models to compare by study arm patient survey data including a) patient costs; b) scores on questions related to patient barriers to TB preventative care; and c) patient satisfaction. Qualitative data will be analysed using appropriate software where open coding will be applied to generate codes and themes. Thematic groupings will be developed and reviewed to identify emergent themes within each domain of the coding framework and quotes that best represent each domain. Thematic interpretation will include collaborative development of a coding framework and detailed coding of transcripts.
5. **Health economics outcomes:** Outcomes include the 1) unit cost per patient accepting and completing 3HP under each delivery strategy (cost analysis) and 2) the incremental cost per disability adjusted life year (**DALY**) averted (cost-utility analysis). The cost analysis will estimate and compare the per-patient cost of delivering 3HP under each strategy and; 2) the cost-utility analysis will identify the economically preferred option if there is a difference in effectiveness between arms (and the more effective option is also the more expensive one). To identify the preferred option, we will assume a willingness to pay of \$500 per DALY averted (as being comparable to other published studies) in the primary analysis. We will estimate the incremental cost per DALY averted of patient choice relative to facilitated DOT or SAT.

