 - a. **All participants:** A standardized checklist-based survey will be used to assess for symptoms of hepatotoxicity or other adverse events (e.g., rash, peripheral neuropathy). The Mulago ISS clinic pharmacy technician will administer the survey at each scheduled clinic visit and at any unscheduled clinic visits if participants present due to concerns about toxicity. Participants with potential adverse events based on the survey will be referred to Mulago ISS clinic clinicians, who will make all decisions regarding further evaluation and treatment continuation or discontinuation. For those with potential symptoms of hepatotoxicity (e.g., abdominal pain, nausea, vomiting, unexplained fatigue or jaundice) this could include a blood draw to assess for elevated liver function tests. Note: women who become pregnant while on 3HP will be recommended to continue and complete 3HP treatment, and will be monitored for side effects as per routine procedures.
 - b. **Facilitated SAT:** In lieu of weekly clinic visits, participants taking 3HP by Facilitated SAT will receive a weekly free (at no cost to them), automated SMS check-in message or IVR phone call asking "Are you well?" (or other similar message, as determined in our formative research phase) with previous instruction to respond "Yes" or "No". All incoming SMS messages will be automatically reimbursed. The Mulago ISS clinic pharmacy technician will receive an automated SMS when a participant responds "No" or does not respond within 24 hours and will call the participant up to three times and ascertain whether he or she is having side effects using the standardized checklist-based survey. Participants who are unable to be contacted by phone will be visited at home by a community health worker (**CHW**). Participants with potential adverse events based on the survey will be referred to Mulago ISS clinic clinicians, who will make all decisions regarding further evaluation and treatment continuation or discontinuation. For those with potential symptoms of hepatotoxicity (e.g., abdominal pain, nausea, vomiting, unexplained fatigue or jaundice) this could include a blood draw to assess for elevated liver function tests.

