^a 3HP treatment may last up to 16 weeks^b Patients randomized to choice arm only^c Time-and-motion studies will be performed on 40 randomly selected days (one day per week throughout the year, stratified by day of week). We anticipate that this will capture up to 250 unique participant visits per arm (750 total).^d Patient costing surveys will include 50 participants from each arm, or 150 participants total^e Only if symptomatic, except at end of follow-up.^f 24 participants/arm

Outcome Measures

Primary Outcome (Effectiveness of delivery options)

Outcome	Numerator	Denominator
Proportion accepting and completing 3HP treatment	Number who take at least 11 of 12 doses within 16 weeks of treatment initiation	Number randomized

Secondary Outcomes (Quantitative)

Outcome	Numerator	Denominator
REACH		
Treatment acceptance	Number taking at least one dose of 3HP	Number randomized
EFFECTIVENESS		
Treatment completion	Number who take at least 11 of 12 doses within 16 weeks of treatment initiation	Number taking at least one dose of 3HP

Cost-effectiveness (overall)	(Cost in Arm A – cost in Arm B) from societal perspective	(DALYs averted in Arm A – DALYs averted in Arm B) from societal perspective
Cost-effectiveness (health system)	As above, but from health system/provider perspective	As above, but from health system/provider perspective
Cost-effectiveness (patient)	As above, but from patient perspective	As above, but from patient perspective
Safety	Number for whom treatment discontinued due to adverse events or intolerance.	Number taking at least one dose of 3HP
Cumulative incidence of TB at 16 months	Number diagnosed with TB during 16-month follow-up	Risk set*
Cumulative incidence of TB at 28 months	Number diagnosed with TB during 28-month follow-up	Risk set*
ADOPTION		
All Participants		
Visit Cost Reimbursement	Number of visits for which reimbursement provided on same day	Total number of DOT/refill visits
Time to complete clinic visit	Mean and median number of minutes for each DOT/refill visit	--
SMS or IVR phone call reminders delivered	Number of SMS or IVR phone call dosing or clinic visit reminders delivered	Total number of SMS reminders scheduled to be sent
SMS or IVR phone call reminders following missed appointments	Number of SMS or IVR phone call dosing or clinic missed appointment reminders delivered	Number of participant weeks with 3HP missed appointments
Screening for active TB	Number screened for active TB during DOT visits	Total number of DOT visits

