- **Primary outcome** analysis will include: 1) unadjusted intent-to-treat comparisons of effectiveness between arms and 2) simple calculation (using the exact binomial confidence intervals) of the effectiveness of each delivery option, with a target of 80%. In these analyses, participants randomized to the choice arm will be treated separately from those randomized to either facilitated DOT or facilitated SAT; the proportion of those in the patient choice arm who choose DOT or SAT will be measured, but the primary outcome will consider all individuals in this arm as randomized to patient choice. Whether 80% acceptance and completion is achieved will be based on the lower bound of the Bonferroni-corrected 98.3% confidence interval exceeding 0.80 in any of the three arms. The intent-to-treat comparisons will use log-binomial regression to calculate prevalence ratios, and Fisher's exact test to determine statistical significance (two-sided alpha of 0.025, including Bonferroni correction). Participants who decline to initiate 3HP after randomization will be counted as not accepting/completing treatment in the primary (intent-to-treat) analysis and will be followed over time for clinical outcomes.
- **Secondary outcome** analysis will include:
 1. **Reach outcomes:** Analysis will include 1) unadjusted comparisons across arms, 2) per protocol analysis of DOT versus SAT in the choice arm in case of crossover including analysis of outcomes among participants who crossed over against outcomes among those who stayed in their originally selected strategy if a sufficiently large number of patients cross over from DOT to SAT or vice versa and 3) simple calculation of the proportion of patients offered 3HP who accept treatment in each arm. We will also compare this outcome across key demographic variables including age, gender, CD4 stratum, and viral load suppression.
 2. **Effectiveness outcomes:** Analysis of effectiveness outcomes will include the development of TB and the occurrence of adverse events analyzed with Chi-square tests, logistic regression, Kaplan-Meier curves, log-rank tests, and Cox regression methods as appropriate. Any signs or symptoms lasting ≥ 3 days duration (by patient self-report) during the previous month will be recorded and included in our analysis. We will also compare outcomes across key demographic variables including age and gender.

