**Secondary Objectives:**

1. To estimate the costs and compare the cost-effectiveness of three strategies for delivering 3HP.
2. To identify processes and contextual factors that influence patient acceptance and completion of 3HP under each delivery strategy.
3. To identify clinic-level barriers to adoption and implementation of 3HP under each delivery strategy.
4. To determine the proportion of patients for whom 3HP treatment is discontinued due to adverse events (**AEs**)/intolerance.
5. To determine the cumulative 16-month incidence of active tuberculosis (**TB**) in each arm.

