### 2.4 Outcomes

The primary outcome assessing the effectiveness of delivery options is the proportion of patients accepting and completing 3HP treatment. Secondary outcomes are classified within RE-AIM domains and are described in full in the trial protocol.

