### 3.8 Interim analysis

1. **Background:** The decision to conduct an interim analysis of trial data and the type of analysis was determined by the Trial Steering Committee (**TSC**), comprised of 3 members not involved in the implementation of the trial nor on the investigative team, and without the Principal Investigators seeing outcome data disaggregated by study arm
2. **Statistical Analysis:** Determination of the timing and the contents of the interim analysis was made in consultation with the study statistician and with input from the TSC. We will calculate and report the proportion (and 95% CI) of patients accepting and completing 3HP treatment within 16 weeks of randomization, aggregated across all study arms. Selected secondary outcomes may also be reported and include treatment acceptance and occurrence of severe adverse events resulting in stopping of 3HP treatment. We will assess outcomes stratified by sex, age, and time on ART. Secondarily, we will take a Bayesian inference approach to estimate the posterior probability that the proportion of patients who accept and complete 3HP, denoted here as  $\theta$ , exceeds 80% in at least one of the three study arms. We will use a Beta distribution to the outcome parameter  $\theta$  and a non-informative flat prior, Beta(1,1), making it such that the prior has little influence on the posterior distribution. We will calculate the posterior probability that  $\theta$  exceeds 0.8 by calculating the size of the tail of the posterior distribution that is above 0.8.

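### SAP 3.7 tests AE occurrence between arms without saying whether that means stopping 3HP for an AE or recorded symptoms, and the symptom checklist is given more often under DOT than under SAT

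*SAP*

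**What the plan says.** The only between-arm safety test in SAP 3.7 is in item 2: "Occurrence of AEs across arms will be assessed using Chi-square tests and logistic regression". No numerator, denominator or alpha is given, and the item does not mention discontinuation or intolerance.

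The Safety row of the protocol's Outcome Measures table has the numerator "Number for whom treatment discontinued due to adverse events or intolerance", with those taking at least one dose as denominator. SAP secondary objective 4 is to determine the "proportion of patients for whom 3HP treatment is discontinued due to adverse events" or intolerance. SAP 2.4 says the secondary outcomes are "described in full in the trial protocol".

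The protocol's Data Analysis section (Effectiveness outcomes) uses the same undefined idea of AE occurrence. It then says that self-reported signs or symptoms lasting at least 3 days "during the previous month will be recorded and included in our analysis".

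On finding AEs, the protocol (Adverse events screening) says the pharmacy technician "will administer the survey at each scheduled clinic visit and at any unscheduled clinic visits if participants present due to concerns about toxicity". Between visits, SAT participants get a weekly automated message asking if they are well. The technician is alerted if the participant answers no or "does not respond within 24 hours and will call the participant up to three times", using the same checklist. A home visit follows if the participant cannot be reached by phone.

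**The concern.** Two endpoints fit the wording of SAP 3.7, and they can give different answers. The trial is open-label, so the choice should not be left until data are in hand.

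The choice matters because the two endpoints are found in different ways. The reason for stopping 3HP is sought in every arm by chart review and by Survey 3. Symptoms are recorded mainly through a checklist whose schedule depends on the delivery mode. A SAT participant who replies that all is well has no checklist that week unless he or she comes in unscheduled. If fewer symptoms are written down under SAT, SAT can look safer with no true difference. The protocol's background section names delayed recognition of adverse events as a possible weakness of SAT, so this is a question on which readers will want a fair answer.

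**Working it through.** The documents give no figure for the AE comparison, so there is none to reproduce.

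**1. Contacts and checklists after day 1** (protocol, Study Arms and Medication administration)

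- DOT: weekly visits for doses 2 to 12, so 11 contacts and 11 scheduled checklists.
- SAT: visits at doses 6 and 12 (2), plus check-ins in weeks 2–5 and 7–11 (9). Contacts = 2 + 9 = 11. Scheduled checklists = 2.
- Let q be the share of check-ins that lead to a completed checklist. SAT checklists = 2 + 9q: 4.25 at q = 0.25, 6.5 at 0.5, 8.75 at 0.75, 11 at 1.
- With 80% attendance at visits in both modes: DOT 0.8 × 11 = 8.8; SAT 1.6 + 9q. SAT passes DOT once q exceeds (8.8 − 1.6)/9 = 0.8. The direction is therefore likely but not certain.

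The documents do not give q.

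**2. How much a symptom test could be distorted**

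Assumptions: the same true AE rate p in all arms; 552 per arm; choice arm split 50:50; one short event per person, spread evenly over treatment; full DOT attendance; a 28-day look-back at each checklist. The protocol speaks of the previous month but ties this to no form.

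- Dose k falls on day 7(k − 1), so dose 6 is day 35 and dose 12 is day 77.
- Two SAT look-backs cover 56 of 77 days. Gap = 21/77 = 27.3%. Weekly DOT visits cover all 77.
- Recorded SAT rate = p × [1 − gap × (1 − r)], where r is the share of the gap recovered by check-ins. Choice is the mean of DOT and SAT.
- At p = 10%, SAT records 7.3% at r = 0, 8.6% at r = 0.5 and 9.3% at r = 0.75.

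False-positive rate of the three-arm Pearson chi-square (2 df, alpha 0.05, 400,000 simulated trials):

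| Setting | r = 0 | r = 0.5 | r = 0.75 | r = 1 |
|---|---|---|---|---|
| p = 5%, 28 days | 15% | 7% | 5% | 5% |
| p = 10%, 28 days | 28% | 10% | 6% | 5% |
| p = 20%, 28 days | 57% | 16% | 8% | 5% |
| p = 10%, 31 days (gap 15/77) | 16% | 7% | 6% | 5% |

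If a 3-day symptom counts when any part of it falls in the look-back, the 28-day gap also drops to 15/77 and the last row applies. With 31 days as well, the gap is 9/77 and the rates at p = 10% are about 9%, 6%, 5% and 5%.

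**3. What testing discontinuation would deliver**

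The protocol (Potential risks to participants) cites 4.9% stopping for adverse effects in an earlier 3HP trial. It is assumed here for DOT.

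- Three arms, 552 each, choice midway, alpha 0.05: power 81% if SAT is 9.8% and 48% if SAT is 2.45%. If 90% start 3HP (497 per arm), 77% and 43%.
- AE occurrence of 10% against 5%, found equally well in all arms: 82%.
- Pairwise, power = Φ[(d − z × se₀)/se₁], where se₀ uses the pooled variance and se₁ the unpooled. For 4.9% against 9%: d = 0.041, se₀ = 0.0153, se₁ = 0.0153, giving 0.765 at two-sided 0.05 and 0.669 at 0.025. For 4.9% against 10%: 0.898 and 0.839. The alpha, which SAP 3.7 does not give, matters.

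**The case against.** A reader might infer that the SAP leaves the protocol's safety outcome untested. The documents do not support that. SAP 2.4 sends the reader to the protocol, whose outcome table has only one AE outcome under Effectiveness, namely discontinuation. Item 2 of SAP 3.7 carries the same heading, so its tests can be read as applying to that outcome. SAP 3.8 also speaks of "occurrence of severe adverse events resulting in stopping of 3HP treatment". Objective 4 asks only for a proportion, and the protocol shares the loose wording, so the two documents do not conflict. The 3-day symptom sentence is in the protocol alone, and SAP 2.3 gives the SAP precedence. All of this stands. It does not settle the meaning, because following SAP 2.4 back to the protocol also leads to the symptom sentence.

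A reader might also infer that DOT participants are contacted about safety more often. They are not: the count is 11 against 11, and the protocol presents the check-ins as a substitute for weekly visits. SAT silence can end in a home visit, whereas after a missed DOT visit the technician is only encouraged to call. The difference lies in how often the full checklist is used.

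Finally, the 28% in the table is not an estimate. It needs no recovery at all from check-ins, events treated as points in time, and perfect DOT attendance. It also ignores that all participants are told to report symptoms at once.

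**Conclusion.** The concern holds in a limited form. SAP 3.7 leaves AE occurrence undefined between two endpoints. If recorded symptoms are meant, the test compares arms whose scheduled checklists differ (11 against 2, plus triggered calls). The resulting bias probably favours SAT. It is about one percentage point of extra false positives at a 10% true rate if check-ins recover three quarters of the gap, and larger if they recover less. Recurrent or persistent symptoms would shrink it; AEs clustered soon after dose 1 would enlarge it. These figures rest on assumed AE rates, timing, look-back and check-in yield, none of which the documents give. If discontinuation was always meant, only the wording needs repair. The primary outcome is unaffected, and the severity is minor.

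**What to change.** Replace the AE part of SAP 3.7 item 2 with text to this effect:

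> Safety: the proportion in whom 3HP is discontinued for adverse events or intolerance, among participants taking at least one dose, will be compared across arms by chi-square test and logistic regression at a stated two-sided alpha. Reasons will be taken from both chart review and Survey 3. Recorded AEs and symptoms will be described by arm, without a significance test, alongside the number of checklist screens completed, noting that scheduled checklists are more frequent under DOT than under SAT.

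This is one paragraph. It keeps the SAP's own tests and uses data the protocol already collects, so it also covers participants already treated. It assumes that completed checklists can be counted from clinic records. The adoption metrics already count side-effect screening at visits and follow-up after negative check-ins.

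The costs are real but modest. There would be no formal test of AE occurrence, and power is lower on a rarer outcome (48% for a halving from 4.9%, against 82% for a halving of a 10% AE rate found equally in all arms). SAT participants are also told to stop the drug if symptoms occur, so discontinuation measures tolerability under each strategy rather than drug toxicity alone. The report should say so.
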